The pathophysiology of intracranial hypertension is complex and depends on the mechanism of cerebral edema, the volume of intracranial contents, the integrity of the BBB, and cerebral perfusion pressure. The balance of Starling forces (the transcapillary hydrostatic pressure gradient that is counterbalanced by an osmotic pressure gradient) determines the magnitude of extracellular fluid flow into the brain substance.

The following issues were considered:

- The etiology of increased brain volume in this patient population has not been established, and the relative contribution of any of the four putative mechanisms, at any single point in the disease process, is unknown. Furthermore, the relative contributions may change over the course of the illness. Since no animal model of CM exists, it is

unlikely that insights into the mechanism of increased brain volume in children with CM will be rapidly forthcoming. Although ongoing research may eventually illuminate the specific mechanisms contributing to the elevated ICP of these patients, our previous work has identified a group of children at high-risk for mortality and broadly effective interventions exist.

- The treatment for increased brain volume that is most likely to be effective in this setting is hypertonic saline.
- Given the rapid reversibility of the increased brain volume, that its etiology is unclear, and that respiratory arrest is the likely cause of death, the other trial arm is ventilatory support.
- Given the high mortality rate in children with CM with highly increased brain volume and the now ready availability of ventilatory support in the ICU in Malawi, those randomized to “usual care” or “hypertonic saline” will receive ‘rescue ventilation’ if they experience a respiratory arrest.

Experimental regimens

Duration of therapy: Serial MRIs have shown that, in survivors, the increased brain volume generally resolves within 48 hours. A summary of data from CM participants on the research ward shows that 85% have either died or been discharged within 72 hours (data not shown). To maximize the chance of observing a positive result, the experimental regimens will continue for 7 days, or until the child experiences death, brain death, or clinical improvement (brain volume score ≤ 5 and Blantyre Coma Score ≥ 3).

Elevation of the head of the bed: In the PICU and PRW, the head of the bed will be elevated to 30°, and the head maintained in the midline with towels.

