1. Arm 1: Usual care + immediate mechanical ventilatory support (VENT) for a maximum of 7 days, with ventilator withdrawal once brain volume has decreased (brain volume score ≤ 5) or the patient has improved clinically (modified Blantyre Coma Score ≥ 3) or the patient dies or meets criteria for severe irreversible neurologic failure.
2. Arm 2: Usual care + intravenous hypertonic saline (HPS) for a maximum of 7 days, withdrawn once brain volume has decreased (brain volume score ≤ 5) and the patient

has improved clinically (Blantyre Coma Score ≥ 3) or the patient dies or meets criteria for severe irreversible neurologic failure.

3. Arm 3: Usual care (UC); intravenous fluids, intravenous artesunate; antipyretics, anticonvulsants and blood transfusions as needed; nutritional support) for a maximum of 7 days, or until brain volume has decreased (brain volume score ≤ 5) and the patient has improved clinically (Blantyre Coma Score ≥ 3) or the patient dies or meets criteria for severe irreversible neurologic failures

Participants will remain in the study throughout their hospitalization and, in survivors, through the 12-month post-randomization follow-up visit. Children are discharged when two sequential 6-hourly blood films are free of malaria parasites, when they have been afebrile for 24 consecutive hours, and when they are able to take medications and food by mouth. Final data collection will be at 12 months post-randomization.

Stratification:

No stratification is required. The ages of retinopathy-positive CM with severely increased brain volume per MRI who survived were compared to those of participants from the same population that died. There was no difference in the age structure (data not shown, $p=0.95$).

Primary and secondary outcomes.

The primary outcome is treatment success or failure, determined within the first 7 days. Treatment success is recovery. Treatment failure is death, ventilatory rescue (for participants in Arms 2 and 3) or meeting criteria for severe irreversible neurologic failure.

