7.6 Unscheduled Visit

Participants will be invited to return to the PRW for any needed medical care in the interim between discharge from the ward and the final study visit at 12 months (\pm 14 days) post-randomization. Any unscheduled visit will be recorded in the participant CRF and may be recorded as an AE or SAE if appropriate.

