- Arm 1: Usual care + immediate ventilatory support for a maximum of 7 days. These subjects will undergo rapid sequence intubation and be placed on a mechanical ventilator to maintain physiological pCO_2 levels for a maximum of 7 days. Arterial blood gas determinations will take place every 3 hours for the first 24 hours, then every 6 hours until the participant is extubated. Non-scheduled blood gas determinations may occur at the discretion of the PICU physician. Participants will remain in the Pediatric ICU during mechanical ventilation and after its discontinuance.
- Arm 2: Usual care + infusion of 3% hypertonic saline to achieve a target blood concentration of 150-160 mmol/L. Participants will remain in the Pediatric ICU during hypertonic saline infusion. Participants randomized to hypertonic saline administration will have electrolytes evaluated on admission and every six hours thereafter until they regain consciousness ($\text{BCS} \geq 3$)
- Arm 3: Usual care (elevation of the head of the bed 30 degrees and intravenous antimalarial drugs).

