9.2 Methods and Timing for Assessing, Recording, and Analyzing Safety Parameters

9.2.1 Adverse Events

ICH E6 defines an adverse event (AE) as any untoward medical occurrence in a participant or clinical investigation subject exposed to an intervention or a pharmaceutical product regardless of its causal relationship to the study treatment. An AE can therefore be any unfavorable and unintended sign (including an abnormal laboratory finding), symptom, or disease, temporally associated with the use of a medicinal (investigational) product. The occurrence of an AE may come to the attention of study personnel during study visits and interviews of a study participant presenting for medical care, or upon review by a study monitor.

Because the safety profiles of the two study interventions are fairly well-defined, and the patient population is critically ill, only AE considered to be possibly attributed to the study intervention will be collected. These will include AE known to be related to the study interventions and pre-specified in 2.4.1.2 and any other unanticipated AE that in the opinion of the investigator was attributed to study interventions. All AEs occurring while on study will be documented appropriately regardless of relationship. All AEs will be followed to adequate resolution.

Any medical condition present at the time that the participant is screened should be considered as baseline and not reported as an AE. However, if the medical condition deteriorates at any time during the study, it will be recorded as an AE.

All AEs will be graded for severity and relationship to study interventions.

Since mortality is an endpoint, death will not routinely be considered an Adverse Event for study purposes. Only events meeting leading to death, hospitalization or prolongation of hospitalization that are outlined in section 2.4.1.2, or that were unanticipated, but that are considered to be possibly related to the study intervention will be reported as SAE.

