9.2.1.3 Expected Adverse Events

All adverse events meeting the criteria listed above will be collected. Special concern will be paid to the following adverse events as they are known side effect of the investigational drugs:

- Potentially attributable to the hypertonic saline intervention:
 - Hypernatremia
 - Hypokalemia
 - Hyperkalemia
 - Phlebitis
- Potentially attributable to the intubation intervention:
 - Pneumothorax
 - Pneumomediastinum
 - Subglottic stenosis
 - Stridor
 - Tracheostomy
 - Bronchospasm
 - Pulmonary hemorrhage

- Respiratory nosocomial infections
- Hypotension
- Endotracheal tube obstruction
- Inadvertent endotracheal tube dislodgment
- Bradycardia induced by vagal response

Adverse Event grading tables (attached as Appendix B) will be used to define these conditions. These events will be captured in the CRF and subsequently in tabular format, listing time of event onset, time of event resolution, brief description of the event, clinician's assessment of severity, and clinician's assessment of relation to the intervention. They will be reported to the local ISM on a monthly basis, and an annual report of these events will be presented to the DSMB, as well as both IRBs. The events will be captured for the duration of the participants' stay on the PICU/PRW, independent of whether the participant is still receiving interventional therapy.

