9.3 Reporting Procedures

9.3.1 Serious Adverse Events

The reporting period for SAEs will be between the time of randomization and the twelve month (± 2 weeks) post-randomization follow up visit.

SAE reporting will be carried out as follows

The study clinician will complete a Serious Adverse Event Form (Appendix D) and SAEs thought to be related to study related procedures will be reported within 24 hours of their recognition, to the independent safety monitor, the IRBs at Michigan State University and the University of Malawi College of Medicine, and the sponsor, unless advised otherwise by the DSMB.

Any AE that meets a protocol-defined serious criterion will be submitted on an SAE form to the DMID Pharmacovigilance Group, at the following address:

DMID Pharmacovigilance Group
Clinical Research Operations and Management Support (CROMS)
[name]
[name]
SAE Hot Line: [name] (US) or [name] (outside US)
SAE FAX [contact] (US) or [name] (outside US)
SAE Email Address: [contact]

Other supporting documentation of the event may be requested by the DMID Pharmacovigilance Group and will be provided as soon as possible.

The DMID medical monitor and clinical protocol manager will be notified of the SAE by the DMID Pharmacovigilance Group. The DMID medical monitor will review and assess the SAE for regulatory reporting and potential impact on study subject safety and protocol conduct.

At any time after completion of the study, if the investigator becomes aware of an SAE that is suspected to be related to study product, the investigator will report the event to the DMID Pharmacovigilance Group, the independent safety monitor, and the IRBs of the University of Malawi and Michigan State University.

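### Capture of the listed expected harms stops at ward discharge (9.2.1.3), which contradicts 9.2.1 and leaves non-serious airway events after discharge without a clear recording rule

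*Combined protocol and SAP*

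**What the plan says.** Several rules bear on when a listed harm is recorded.

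- **9.2.1.3** names the events of special concern for each intervention, including stridor, subglottic stenosis, tracheostomy and respiratory nosocomial infection for intubation. It then says "The events will be captured for the duration of the participants' stay on the PICU/PRW", whether or not the child is still receiving the intervention.
- **9.2.1** gives two instructions in one paragraph: "only AE considered to be possibly attributed to the study intervention will be collected" and then "All AEs occurring while on study will be documented appropriately regardless of relationship".
- **Section 4** fixes what being on study means: "Participants will remain in the study throughout their hospitalization and, in survivors, through the 12-month post-randomization follow-up visit".
- **9.3.1** covers serious events: "The reporting period for SAEs will be between the time of randomization and the twelve month" visit.
- **7.6** enters every unscheduled visit in the CRF, but says only that it "may be recorded as an AE or SAE if appropriate".
- **7.3 and Appendix A** schedule history and physical examination at follow-up visits, the first at 1 month. **9.4** follows recorded AEs to resolution.

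On length of stay, 2.3 reports that on the research ward "85% have either died or been discharged within 72 hours". Section 8.1 describes Arm 1 as "Usual care + immediate ventilatory support for a maximum of 7 days", with the child staying in the PICU after ventilation stops.

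**The concern.** Secondary Objective 3 is to assess the safety of early ventilation and of hypertonic saline, and under 9.6 the DSMB reviews safety data for each arm. That review needs a known observation period for the listed harms. Here the period is either the ward stay or the whole study, depending on which section staff follow. If they follow 9.2.1.3, it ends on a day set by the child's recovery, which the intervention itself may shift. It may also end before a mild airway complication shows. Section 2.4.1.3 itself warns that ventilation harms can persist and be severe.

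Two things are at stake: milder airway harm may be under-recorded, and in-hospital proportions may partly reflect how long each child was watched.

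**Working it through.** The plan gives no figure to reproduce. The check sets the rules side by side and asks which of them would pick up a new, non-serious listed event after discharge.

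**Step 1. Windows**

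| Section | Covers | Period | New non-serious event after discharge? |
|---|---|---|---|
| 9.2.1.3 | Listed expected events | PICU/PRW stay | No |
| 9.2.1 | All AEs (or only possibly attributed ones) | While on study, to 12 months in survivors (Section 4) | Yes, against 9.2.1.3 |
| 9.3.1 | SAEs | Randomisation to 12 months | No, serious only |
| 7.6 | Unscheduled visits | Discharge to 12 months | Only if the family returns; AE classification optional |
| 9.4 | AEs already recorded | To resolution | No, follow-up rather than detection |
| 7.3, Appendix A | History and examination | 1, 6 and 12 months | Possible, but no instruction to ask about the listed events |

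The first two rows conflict, and no other row settles the matter.

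**Step 2. Size of the window.** Take 12 months as 365 days. A 72-hour stay covers 3/365 = 0.8% of the study period. A 7-day stay covers 7/365 = 1.9%. If stays ranged from 3 to 7 days, windows would differ between children by up to 7/3 = 2.3-fold. Three days is the past typical stay and seven days is the ventilation maximum; neither is a stay by arm.

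**Step 3. Does stay depend on arm?** Section 4 applies one discharge rule to all children: two clear blood films, 24 hours without fever, and the ability to take food and medicines by mouth. A child cannot meet the last condition while intubated, so a common rule does not guarantee a common stay. A longer stay in Arm 1 is plausible, but it is an inference.

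**Step 4. Which events are sensitive?**
- Tube obstruction and dislodgement, electrolyte changes and phlebitis arise during treatment. The discharge cut-off hardly touches them.
- Hypotension and bradycardia are graded in Appendix B against pre-intubation values. They do not accrue with ward days.
- Nosocomial infection does depend on time. The intubated cohort cited in 2.2.2.1 had cumulative incidences of 2.3% after 48 hours, 15.3% after 72 and 26.6% after 92, a rise of 26.6 − 15.3 = 11.3 percentage points between the last two times.
- Stridor and mild stenosis symptoms can first appear after discharge.

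**Step 5. Is a serious late airway event safe?** Mostly. Readmission meets the general seriousness criteria in 9.2.3, and 9.2.3.1 covers life-threatening events attributable to an intervention. But 9.2.1 limits reported SAEs to events in 2.4.1.2 or unanticipated events. Section 2.4.1.2 lists only hypertonic saline risks; ventilation risks are in 2.4.1.3 and are expected under 9.2.1.3. Read literally, an expected late airway event passes neither test. Section 9.2.3 cites 2.4.1.2 in the same way, though its list can be read more loosely.

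**The case against.** The best defence is that capture after discharge exists. SAEs run to 12 months, unscheduled visits enter the CRF, recorded AEs are followed to resolution, and examinations are scheduled. The 9.2.1.3 sentence read in full can be taken as extending capture beyond the end of treatment. Appendix B grades mild stenosis by racemic epinephrine after extubation, which mostly happens while the child is still in the PICU; the higher grades involve reintubation, surgery or tracheostomy and would normally be serious. Section 9.1 makes survival the primary safety parameter and adds long-term neurological sequelae, and neither depends on this window.

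Most of that stands, and it rules out three stronger readings that a reader might infer.

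- **That late airway harm goes uncounted.** The SAE period in 9.3.1 contradicts this, although the 2.4.1.2 reference leaves the reporting of some serious airway events uncertain.
- **That the windows demonstrably differ by arm and bias the comparison by a calculable amount.** No stay by arm is given. Section 2.3 says swelling in survivors generally resolves within 48 hours, and median ventilation in the cited cohort was 36 hours, though with 60% mortality. Any excess computed from assumed stays and daily risks would rest on the assumptions alone.
- **That a longer stay inflates the listed harms in general.** Step 4 shows that few of them behave this way, and more infection from longer ventilation would be a genuine harm, not an artefact.

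The defence does not remove the conflict between 9.2.1 and 9.2.1.3, or the lack of any instruction to look for non-serious airway events once the child has gone home.

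**Conclusion.** The point holds in a narrow form. Two sections set incompatible capture periods for the same events, and the shorter one is tied to length of stay. The clear loss is non-serious airway events, mainly stridor or mild stenosis symptoms, that first appear after discharge. Dependence on stay matters mainly for nosocomial infection. The number of events affected cannot be estimated from the documents; the 0.8%, 1.9% and 2.3-fold figures describe window length under assumed stays of 3 and 7 days, not bias. That ventilation lengthens stay is a plausible assumption. The primary outcome is unaffected. This is an inexpensive improvement to safety ascertainment for Secondary Objective 3, and not a flaw that undermines the trial.

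**What to change.** 1. **9.2.1.3 and 9.2.1:** set one capture window for the listed events, from randomisation to the 1-month visit, for every randomised child whatever the discharge date. Include Arms 2 and 3, where rescue ventilation carries the same airway risks. Resolve the two competing collection rules in 9.2.1 at the same time.
2. **9.3.1:** keep the 12-month period for serious events and state how it relates to the window above.
3. **7.6:** say that a listed event found at an unscheduled visit within the window will be recorded as an AE.
4. **1-month visit form:** ask about stridor, breathing difficulty, readmission and airway procedures since discharge.
5. **Reporting:** tabulate the listed events by arm over the fixed window, with the number of children who died or missed the visit. The ±14-day tolerance makes the end date vary slightly, but it is tied to the visit schedule and not to the stay.
6. **9.2.1 and 9.2.3:** extend each reference to 2.4.1.2 so that it also covers 2.4.1.3.

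The cost is a few form questions, one table and some parental recall error between discharge and the visit. No treatment rule changes.

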9.2.2 Reactogenicity (for Vaccine Studies and Some Therapeutic Trials)

NA

9.2.3 Serious Adverse Events

An adverse event or suspected adverse reaction is considered "serious" if, in the view of either the investigator or sponsor, it results in any of the following outcomes:

- Death,
- A life-threatening adverse event,
- Hospitalization or prolongation of existing hospitalization,
- A persistent or significant incapacity or substantial disruption of the ability to conduct normal life functions, or
- A congenital anomaly/birth defect.

Important medical events that may not result in death, be life-threatening, or require hospitalizations may be considered serious when, based upon appropriate medical judgment they may jeopardize the participant and may require medical or surgical intervention to prevent one of the outcomes listed in this definition. Only events that are not attributable to the malarial illness, that are outlined in section 2.4.1.2, or that were unanticipated, but that are considered to be possibly related to the study intervention will be graded and reported as Adverse Events to the sponsor, IRBs, and independent safety monitors.

- Life-threatening adverse event: An adverse event is considered “life-threatening” if, in the view of either the investigator or sponsor, its occurrence places the participant or subject at immediate risk of death. It does not include an adverse event, had it occurred in a more severe form, might have caused death.

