2.4.1.2 Hypertonic saline

The known side-effects of hypertonic saline include:

- Hypernatremia
- Hypokalemia
- Rebound cerebral edema upon termination of therapy

These conditions are all a direct result of the increased sodium and osmolarity that are also the goal of the intervention. Assiduous monitoring of electrolytes (as described in 9.2.4) will therefore be undertaken to balance desired effects with possible side effects.

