2.4.1.3 Assisted ventilation

Mechanical ventilation via an endotracheal tube has a number of associated risks which can be broadly classified into following categories²⁴⁶

- Adverse effects of positive pressure, volume and flow:
 - Pneumothorax
 - Pneumomediastinum
 - Hypotension
 - Bronchospasm
 - Pulmonary hemorrhage
- Adverse effects of endotracheal intubation
 - Endotracheal tube obstruction
 - Inadvertent endotracheal tube dislodgment
 - Bradycardia induced by vagal response
 - Mucosal inflammation
 - Stridor
 - Subglottic stenosis
 - Respiratory nosocomial infections

These events may be persistent and severe, necessitating tracheostomy.

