9.5 Halting Rules

The following eventuality would trigger temporary suspension of enrollment until a safety review is convened and further evaluation undertaken:

- Five subjects where current HPS regimen is unable to achieve the target Na⁺ levels of 150-160 mmol/L.
- Any SAE deemed to be related to each of the experimental medical interventions (ventilator support or infusion of 3% hypertonic saline solution).

DMID retains the authority to suspend additional enrollment and study interventions during the entire study, as applicable.

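### The AE-collection and SAE-reporting clauses cite only the hypertonic-saline risk list, so the SAE route for some serious ventilation complications is contradictory

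*Combined protocol and SAP*

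**What the plan says.** Three clauses decide which adverse events are collected or reported.

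- **Collection, 9.2.1.** Only AEs possibly attributed to the intervention are collected: "These will include AE known to be related to the study interventions and pre-specified in 2.4.1.2 and any other unanticipated AE". Shortly afterwards the same section says "All AEs occurring while on study will be documented appropriately regardless of relationship".
- **SAE reporting, 9.2.1.** "Only events meeting leading to death, hospitalization or prolongation of hospitalization that are outlined in section 2.4.1.2, or that were unanticipated", and that are possibly related to the intervention, are reported as SAEs.
- **Reporting, 9.2.3.** After excluding events due to malaria, the sentence refers to events "that are outlined in section 2.4.1.2, or that were unanticipated, but that are considered to be possibly related to the study intervention". These "will be graded and reported as Adverse Events to the sponsor, IRBs, and independent safety monitors".

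Section 2.4.1.2 concerns one intervention: "The known side-effects of hypertonic saline include" hypernatremia, hypokalemia and rebound cerebral edema. Ventilation has its own list in 2.4.1.3: "Mechanical ventilation via an endotracheal tube has a number of associated risks".

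Four other provisions bear on the point.

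- **9.2.1.3** lists expected events for both interventions and sends them monthly to the local safety monitor and annually to the DSMB and both IRBs.
- **9.2.3.1** defines protocol SAEs without regard to arm.
- **9.3.1** requires SAEs thought to be related to study procedures to be reported within 24 hours to the safety monitor, the IRBs and the sponsor.
- **9.5** suspends enrollment on "Any SAE deemed to be related to each of the experimental medical interventions", and names ventilator support as one of them.

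**The concern.** The two reporting clauses are restrictive. An event must be on the saline list or be unanticipated, and must be possibly related. A known complication of intubation or ventilation is on a different list, and because it is listed it is anticipated. On the face of the 9.2.1 clause it therefore has no route to being reported as an SAE.

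The safety of early ventilation is Secondary Objective 3, the trial is open-label, and 32 VENT children are projected. Enrollment is suspended on a single related SAE, so whether one serious event is classed as an SAE can decide whether a safety review is convened. If site staff apply 9.2.1 as written, some serious ventilation events would appear only in periodic summaries, and 9.2.1.3 does not name the sponsor among the recipients of those summaries.

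**Working it through.** The plan states no figure to reproduce. The check is a count of the lists and a comparison of the clauses.

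1. **Which list is cited.** All 3 of the clauses cite 2.4.1.2; 0 of 3 cite 2.4.1.3.

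2. **What the lists hold.**
   - 2.4.1.2: 3 saline effects.
   - 2.4.1.3: 5 effects of pressure, volume and flow + 7 effects of intubation = 12.
   - 9.2.1.3, intubation: 12 − 1 (mucosal inflammation is absent) + 1 (tracheostomy is added) = 12 items, 11 of them shared with 2.4.1.3.
   - 9.2.1.3, saline: 4 items, of which 2 (hyperkalemia and phlebitis) are not in 2.4.1.2.

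3. **The 9.2.1 SAE clause applied to one event in each arm.** Suppose a related pneumothorax in the VENT arm lengthens the stay by 7 days or less. It is not in 2.4.1.2, and it is not unanticipated, so it is not reported as an SAE. Suppose a related hypokalemia in the saline arm lengthens the stay equally. It is in 2.4.1.2, so it is reported.

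4. **What the other sections recover.** For an anticipated, related ventilation complication named in 9.2.1.3:

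| How the event is serious | 9.2.1 SAE clause | Protocol SAE under 9.2.3.1 | Periodic summary, 9.2.1.3 |
|---|---|---|---|
| Life-threatening and not a study outcome | Not reported | Yes | Yes |
| Death other than by respiratory arrest from intracranial hypertension | Not reported | Yes | Yes |
| Stay prolonged by more than 7 days | Not reported | Yes | Yes |
| Stay prolonged by 7 days or less | Not reported | No | Yes |
| Lasting incapacity | Not reported | No | Yes |
| Important medical event | Not reported | No | Yes |

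The first three rows reach the sponsor's pharmacovigilance group through 9.3.1. The last three do not meet a protocol-defined criterion, yet 9.2.3 makes or allows them to be serious.

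5. **The contradiction.** For the last three rows, 9.3.1 calls for a report within 24 hours if the event is thought related to study procedures, while 9.2.1 says the event is not reported as an SAE. Staff cannot follow both. The trigger in 9.5 depends on which one they follow.

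6. **A limit on the difference between arms.** The 9.2.1 SAE clause names only death, hospitalization and prolonged hospitalization as outcomes. Lasting incapacity and important medical events are therefore outside its wording for saline too. The clean difference between the arms is the shorter prolongation of stay.

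**The case against.** The strongest reply is that the plan reports ventilation events by other routes.

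- **Summaries.** 9.2.1.3 is itself a reporting rule, shared by both interventions, and covers 11 of the 12 complications. A reader might infer from the clauses that all 12 escape reporting; the documents do not support that. What 9.2.1.3 lacks is an expedited route and the sponsor as a recipient. It also opens by referring back to the criteria above it, which are the incomplete ones.
- **Routes that do not depend on arm.** 9.2.3.1 and 9.3.1 do not cite 2.4.1.2, and Section 4 (Safety monitoring) says the safety monitors are told of all SAEs. This stands for the first three rows of the table. For the others it shows the conflict with 9.2.1 and does not resolve it.
- **Halting rule.** 9.5 names ventilator support, and Appendix B has rows for 8 of the 12 complications. A reader might infer that the rule could never fire for VENT. That is too strong, because life-threatening events, some deaths and long prolongations can still trigger it.
- **Grammar of 9.2.3.** The sentence can be read as a list of three alternatives, the first being any event not attributable to malaria. On that reading a ventilator pneumothorax qualifies. This is a fair reading of 9.2.3, but the SAE clause of 9.2.1 has no such item.
- **Not purely a matter of arm.** The same clauses omit two expected saline events, hyperkalemia and phlebitis. This is correct, and it widens the fix.

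A reader might also size the gap from the ventilation cohort in 2.2.2.1: 20/61 = 33% with hospital-acquired infection, or about 10 of 32 VENT children. That figure does not measure the gap. The denominator is children who survived more than two days, out of 83 intubated. Eight of the 20 had septicemia, which 2.4.1.3 does not list. The infections were not necessarily serious, and respiratory ones are already in the 9.2.1.3 summaries.

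**Conclusion.** The point holds as an internal inconsistency in the safety-reporting text. Three clauses cite an incomplete list. As a result, an anticipated, related ventilation complication that is serious but outside 9.2.3.1 is not an SAE report under 9.2.1, although 9.3.1 requires one within 24 hours. Such an event might not trigger 9.5.

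The affected set is narrow, namely the last three rows of the table. The documents give no rate for such events, so no count of children can be stated. The primary analysis is not affected.

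The conclusion rests on reading the clauses literally and on the event being judged both related and anticipated. That the omission is an unfinished cross-reference is an inference: Section 4 cites the saline and ventilation risk sections side by side, under the numbers 2.3.1.2 and 2.3.1.3. The correction should be made because it is nearly free and the rule is operative.

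**What to change.** In the AE-collection and SAE-reporting clauses of 9.2.1 and the reporting clause of 9.2.3, replace the reference to section 2.4.1.2 with one to sections 2.4.1.2, 2.4.1.3 and 9.2.1.3. Adding 2.4.1.3 alone would still leave out hyperkalemia and phlebitis; 9.2.1.3 supplies them.

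In the same amendment:

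- reconcile the three clauses with 9.2.3.1 and 9.3.1, so that it is clear which serious, related events go out within 24 hours and which go only into the summaries. This includes deciding whether the outcomes named in the 9.2.1 SAE clause are meant to be narrower than the seriousness criteria of 9.2.3;
- reconcile the restriction on collection with the statement that all AEs are documented whatever their relationship;
- punctuate the 9.2.3 sentence so that it has one reading.

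The cost is a short text amendment and its IRB review. Treatment, sample size and analysis are unchanged.
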